9.2 Secondary study parameter- VAS scores for satiety and GI symptoms

Secondary parameters include differences between treatments in feelings of satiety (as measured by VAS) and GI symptoms (as measured by VAS). During each of the test days, participants (n=35) fill in nine VAS scores (VAS1-VAS9) per time point, at 12 time points ($t= 0, 30, 60, 90, 105, 120, 135, 150, 165, 180, 195, 210$ min). If the VAS data is normally distributed and homogeneity of variance holds, we will use a repeated measures analysis of variance (ANOVA) model that includes the fixed factors treatment, time, and the interaction treatment * time to evaluate the null hypothesis that there is no difference in VAS scores after control and active yoghurt (n=35, $p \leq 0.05$). If the results of the ANOVA indicate a significant effect of intervention yoghurt (Wilks' Lambda test, $p \leq 0.05$), the treatments will be compared based on pairwise comparison with a Tukey post hoc test.

Missing values of the secondary study parameter will cause the intervention to be left out, due to the use of ANOVA.

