6.5 Description and justification of route of administration

The lipids will not be administered *via* an ileal catheter, as the effectiveness of this administration route has been proven already in previous studies (for an overview of studies, we refer to the review [3]). For an effective weight management strategy, administration should be performed *via* the normal route of food intake: oral administration. The current study will focus on the ability of lipid to induce the ileal brake when given orally. The lipids will be mixed with yoghurt, not only to allow easy consumption for the participants, but also to ensure no difference in appearance between control and active formulation. The lipids from the active intervention yoghurt will be delivered into the more distal small intestine within the two hours between ingestion and meal intake, and might consequently activate the ileal brake, whereas the control intervention yoghurt will deliver nutrients more proximally (to the stomach and duodenum). This allows investigating the effects of distal small intestinal delivery of undigested nutrients on food intake.

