7.1.2 Secondary study parameters/endpoints

Feelings of satiety (VAS scores)

The secondary study parameter is the effectivity to activate the ileal brake and, hence, induce feelings of satiety and reduce feelings of hunger, as measured on VAS scores (satiety, fullness, hunger, desire to eat, desire to snack). The VAS scores will be compared in time between intervention and control within a subject.

GI symptoms (VAS scores)

Another secondary study parameter is the occurrence and severity of gastrointestinal (GI) symptoms that orally ingested lipid encapsulates might give, as measured on VAS scores of GI symptoms (bloating, discomfort, pain, nausea). The VAS scores will be compared in time between intervention and control within a subject. Besides, the number of AEs and SAEs will be recorded. Moreover, we will assess whether differences in GI symptoms relate to encapsulate type.

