Interview	Sign consent , complete screening (inclusion); and information lecture	Screening questionnaire, height, body weight
Test days (2x)		
8:50 am	Arrival* and baseline	VAS (S & GI, t=0 min)**
9:00 am	Standardized breakfast(t=0 min)	
9:30 am		VAS (S & GI, t=30 min)
10:00 am		VAS (S & GI, t=60 min)
10:30 am	Intervention yoghurt(t=90 min)	VAS (S & GI, t=90 min)**
10:45 am		VAS (S & GI, t=105 min)
11:00 am		VAS (S & GI, t=120 min)
11:15 am		VAS (S & GI, t=135 min)
11:30 am		VAS (S & GI, t=150 min)
11:45 am		VAS (S & GI, t=165 min)
12:00 am		VAS (S & GI, t=180 min)
12:15 am		VAS (S & GI, t=195 min)
12:30 am	Ad libitum lunch(t=210 min)	VAS (S & GI, t=210 min)**
13:00 am	Return home	

VAS= Visual Analogue Scales for satiety (S) and GI symptoms (GI). * after 10 h fasting. ** VAS score measured just before the intervention.

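### The treatment main effect in the VAS analysis averages in four pre-yoghurt scores, so it estimates only 8/12 of a constant post-yoghurt effect; a baseline-adjusted post-yoghurt contrast is a cheap improvement for these secondary endpoints

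*Combined protocol and SAP*

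**What the plan says.** Section 9.2 has participants "fill in nine VAS scores (VAS1-VAS9) per time point, at 12 time points", from t=0 to t=210 min. It analyses them with a "repeated measures analysis of variance (ANOVA) model that includes the fixed factors treatment, time, and the interaction treatment * time", in order "to evaluate the null hypothesis that there is no difference in VAS scores after control and active yoghurt". The follow-up step is conditional: "If the results of the ANOVA indicate a significant effect of intervention yoghurt" by Wilks' Lambda, a Tukey comparison is made. On incomplete data it says: "Missing values of the secondary study parameter will cause the intervention to be left out, due to the use of ANOVA".

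Table 3 in section 7.3 places the yoghurt at t=90 and footnotes that score as "VAS score measured just before the intervention". Section 7.1.2 adds only this: "The VAS scores will be compared in time between intervention and control within a subject". No post-yoghurt window, baseline covariate or change score is stated. Section 9 lists test day (1, 2) among the fixed variables, but the model in 9.2 does not contain it.

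**The concern.** The null hypothesis is about scores after the yoghurt, but a third of the modelled scores come before it. With test days at least a week apart, no treatment difference is expected at t=0 to 90. Those four times pull the treatment main effect towards zero, and the information they carry about the subject's state that day is not used as a baseline.

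The trigger for follow-up can be read as the treatment main effect or as treatment by time. If the main effect decides, a real difference in satiety or GI symptoms is easier to miss. If the interaction decides, the chance of detection depends heavily on how strongly scores correlate within a day, which the documents do not report.

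**Working it through.** **The plan's only power figure.** Section 4.4 concerns food intake. (156/82)² × (1.96 + 0.84)² = 28.4, so 29 subjects; with t-values, (156/82)² × (2.048 + 0.855)² = 30.5, and iteration settles at 30.4, so 31. This reproduces the plan. Nothing comparable exists for VAS, so the power figures below are relative.

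**Dilution (no assumption about correlation).** In a balanced within-subject ANOVA, the treatment main effect is the paired test on each subject's active-control difference averaged equally over the 12 times. With a constant post-yoghurt effect D, this is (4 × 0 + 8 × D)/12 = 0.67D. If the effect were present only at t=165 to 210, it would be 4/12 = 0.33 of that effect; an eight-time post-yoghurt mean would recover 4/8 = 0.50.

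**Power set-up (assumed).** Set the SD of a single active-control difference to 1. The correlation between times is either equal (r) or decays exponentially with the stated time constant. D is scaled so that the unadjusted mean of the eight post-yoghurt differences has 80% power at n=35, two-sided 0.05 (noncentrality 2.884 on 34 df). V8 and V12 are the variances of the 8- and 12-time means; R is the correlation between the pre-yoghurt and post-yoghurt means.

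- Main effect: noncentrality 2.884 × (8/12) × √(V8/V12), 34 df.
- Treatment by time: noncentral F on 11 and 24 df. With equal correlation, λ = 2.884² × V8 × (8 × 4/12)/(1 − r).
- Adjusted post-yoghurt mean: noncentrality 2.884/√[(1 − R²)(1 + 1/32)], 33 df.

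Worked case, r = 0.5: V8 = (1 + 7 × 0.5)/8 = 0.5625; V12 = (1 + 11 × 0.5)/12 = 0.5417; the variance of the four-time pre-yoghurt mean is (1 + 3 × 0.5)/4 = 0.625; R² = 0.25/(0.625 × 0.5625) = 0.711.

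- Main effect: 2.884 × 0.667 × 1.019 = 1.96, power 47.8%.
- Treatment by time: λ = 8.317 × 0.5625 × 2.667/0.5 = 24.9, power 81.4%.
- Adjusted mean: 2.884/√(0.289 × 1.031) = 5.28, power 99.9%.

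Power (%) at n=35:

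| Same-day correlation | Main effect, constant | Treatment × time, constant | Adjusted mean, constant | Treatment × time, late | Adjusted mean, late |
|---|---|---|---|---|---|
| r = 0 | 62.8 | 11.5 | 78.7 | 11.5 | 28.1 |
| r = 0.2 | 50.9 | 30.1 | 92.2 | 30.1 | 39.3 |
| r = 0.3 | 49.3 | 44.9 | 97.1 | 44.9 | 48.7 |
| r = 0.5 | 47.8 | 81.4 | 99.9 | 81.4 | 72.7 |
| r = 0.7 | 47.0 | 99.6 | >99 | 99.6 | 95.4 |
| r = 0.9 | 46.5 | >99 | >99 | >99 | >99 |
| 30-min decay | 63.9 | 23.9 | 80.0 | 22.2 | 28.9 |
| 60-min decay | 59.5 | 46.6 | 83.9 | 45.4 | 31.4 |
| 120-min decay | 54.5 | 85.6 | 91.8 | 85.4 | 38.8 |
| 240-min decay | 50.9 | 99.8 | 98.5 | 99.8 | 54.1 |

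"Late" means the same height, but only at t=165 to 210; there the main effect has 15-21%. To regain 80% for a constant effect, the main effect would need 51-76 subjects. Scaled at n=31 instead, its power is again 47-64% and it would need 45-67. In simulation (10,000 trials per structure), the adjusted test rejected a true null in 4.5-5.3% of trials. These figures leave out a test-day term, which costs one further degree of freedom.

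**Missing scores.** Each attribute has 2 × 12 = 24 scores per subject. If 0.1% were missing at random (assumed), 35 × (1 − 0.999²⁴) = 0.83 subjects would be incomplete per attribute.

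**The case against.** The strongest reply is that the plan already contains an undiluted term. Treatment by time responds to a difference that appears only after t=90. Two cues suggest that it may be the intended test: section 7.1.2 compares scores in time, and Wilks' Lambda adds nothing to the ordinary F-test for a two-level factor. A reader might infer from the dilution that the plan cannot see a post-yoghurt effect. The documents do not support that, nor do they say that the main effect decides.

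A reader might also infer that the adjusted mean is the better test whatever the truth. It is not. Sections 1 and 6.2 describe in vitro lipolysis delayed by up to four hours, and section 6.5 expects lipid to be "delivered into the more distal small intestine within the two hours between ingestion and meal intake", so a late effect is plausible. For an effect confined to t=165 to 210, treatment by time is stronger in five of the ten structures, by up to 47 points (85.4% against 38.8% at 120-minute decay). Even for a constant effect, some other strongly serial patterns favour it over adjustment for the pre-yoghurt mean: at n=31 with an assumed effect of 0.3 SD, 83% against 78% and 98% against 93%. Adjusting for the t=90 score alone gave 91% and 98% there.

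What survives is narrower. Treatment by time is weak at low correlation, spends 11 degrees of freedom, gives no single effect estimate and is not named as decisive. The adjusted mean beats the main effect in all ten structures, for constant and late effects alike.

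**Conclusion.** The point holds as a modest gain in efficiency and clarity. The 8/12 factor follows from the schedule and the model, given a constant post-yoghurt effect and none before it. The power comparison (47-64% for the main effect against 79% to over 99% for the adjusted post-yoghurt mean) rests on assumed correlations and a constant effect. Treatment by time covers part of the gap, but has only about 12-47% power for a constant effect at correlation 0-0.3 or 30- to 60-minute decay.

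A reader might infer bias under the null or an inflated error rate; the 12-time model causes neither in either term. Only if both terms could open the follow-up, each at 0.05, would it open falsely in about 1 − 0.95² = 9.75% of trials per attribute, and section 9.2 does not say that they may. The missing-score rule discards valid data, but the loss is probably small because forms are collected on site. The endpoints are secondary, the study is explorative, and the paired t-test on food intake is untouched.

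**What to change.** Reword section 9.2 so that, for each attribute:

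- **Deciding test:** the mean active-control difference over t=105 to 210, two-sided 0.05. It comes from a linear mixed model of all available scores at those eight times. Fixed effects are subject, test day (1, 2), treatment, time, treatment by time and the same-day pre-yoghurt score; test day within subject is a random effect. State in advance whether the covariate is the mean of t=0 to 90 or the t=90 score.
- **Supporting test for a late effect:** treatment by time. Use either the mixed model's own F-test, with a same-day covariance that allows serial correlation, or a separate complete-case repeated measures ANOVA if Wilks' Lambda is kept. Wilks' Lambda is not a test from a mixed model on all available scores.
- **Deletions:** drop the Tukey step, which repeats the treatment comparison when two treatments are pooled over time. Limit the missing-value rule to any complete-case supporting test.

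Two model terms matter. With subject as the only random effect, same-day scores count as independent, and the simulated null rejection rate was 23-58% whenever they were correlated. With subject random rather than fixed, stable differences between subjects can distort the covariate slope: power was 44% instead of 79% at correlation 0 in one assumed case.

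The cost is analysis wording and slightly more work; all scores are already collected, and SPSS can fit the model. About 1-2 points of power are lost against an unadjusted post-yoghurt mean if same-day scores are uncorrelated. For a late effect, the deciding test is weaker than treatment by time in some correlation structures, which is why that term stays.

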This leads, after a small number of iterations, to a re-estimate of n of at least 31 subjects ($n \geq 30.4$). According to this power calculation, 31 subjects will need to complete the study. Because of possible dropouts, 35 subjects will be recruited for this study.

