7.2 Randomisation, blinding and treatment allocation

All 35 participants receive two treatments of one day each, following a cross-over design. The order in which they receive the treatments will be determined through randomisation. Randomisation will minimize the risk of bias and enhance the validity of statistical comparisons. As subjects qualify for the study, they will be assigned a subject number (01 - 35, *via* lottery) that corresponds with a predefined randomization schedule.

Blinding of packing and treatment will be assured for subjects. We will check at the end of the last test day whether the subjects were expecting to consume a control on one or more of the test days, and in case yes, on which day(s) they received it. Besides, on this day we will ask how they liked the yoghurts.

The VAS questionnaires will be labelled by the researcher with study title (Lipid encapsulates, LE), subject number (01-35), yoghurt (A, B) and time point (t= 0, 30, 60, 90, 105, 120, 135, 150, 165, 180, 195, 210 min). For example: LE07/ A / 120 - Subject 07, active yoghurt, VAS scores at 120 minutes.

Besides, labelling of the products will be according to the following code: study title (Lipid encapsulates, LE), subject number (01-35), yoghurt (A, B), and date. For example: LE07/A 13-02-17 means subject 7 of lipid encapsulates study-yoghurt A (active) produced on February 13th 2017.

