Upon arrival at Maastricht University (8:50 am), compliance to the previously mentioned rules will be checked and baseline measurements will be done ("t=0" min), including nine VAS scores for satiety and GI symptoms. Then, the experiment starts with the ingestion of a standardized breakfast (9:00 am, t=0 min). During all study days, this breakfast will be relatively light (± 120 kcal) and low in fat (≤ 0.5 g total lipid): 1 sandwich (tijgerbrood tarwe 1 g lipid/100g, 1 boterham: 35g (± 84 kcal)) with marmalade (0 g lipid/100g, 1 portion: 15g (± 36 kcal)) and one glass of water or tea (150 mL).

Ninety minutes after breakfast (10:30 am, t=90 min), once major part of the breakfast has been emptied from the stomach, subjects receive a low-fat yoghurt-like product of 0.20 L that contains one of the two formulations of emulsified safflower oil (6 g lipid as active or control formulation, for product details see section 5), following a randomized cross-over design. Each 30 minutes before the intervention and each 15 minutes after the intervention, the nine VAS scores for satiety and GI symptoms will be measured. Two hours after the intervention yoghurt (12:30, t=210 min), *ad libitum* meal intake will be measured as amount eaten from a large pasta meal (>1 kg, obtained from a local supermarket). After collection of these results, the test day is finished and the subject returns home (around 13:00 am). For an overview of the complete study design, see Figure 1.

VAS scores for satiety and GI symptoms- During a test day, satiety and GI symptoms will be measured at 12 time points (t= 0, 30, 60, 90, 105, 120, 135, 150, 165, 180, 195, 210 min). Questionnaires will be used to measure satiety feelings (satiety, fullness, hunger, desire to eat, desire to snack) and GI symptoms (bloating, discomfort, pain, nausea). These nine attributes will be measured using Visual Analogue Scales (VAS, 0 to 100 mm) scores, with the most negative or lowest intensity feelings at the low end and the opposing terms at the high end. The subject will be asked to indicate his feeling at that moment. The investigator can easily quantify the rating as shown in previous studies (for example: METC 13-2-025; 11-3-034; 14-3-062). The scoring forms will be collected immediately so that they cannot be used as a reference for later scorings.

Table 3. Schedule of the participant prior and during the test days.

When?	Action/Intervention	Measurement

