8.2 AEs, SAEs and SUSARs

8.2.1 Adverse events (AEs)

AEs are defined as any undesirable experience occurring to a subject during the study, whether or not considered related to the investigational product, trial procedure, or the experimental intervention. All AEs reported spontaneously by the subject or observed by the investigator or his staff will be recorded.

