10.2 Recruitment and consent

Subjects will be recruited from a pool of previously included subjects that participated in previous studies, and besides, using posters at the local libraries and student frequented areas, advertising in local newspapers, and if needed using www.onderzoeksmachine.nl. Initial information will be provided verbally or *via* email. The written information brochure will be send by regular mail or email. If a volunteer is interested, an appointment will be made to sign an informed consent and complete the medical screening (for the procedure see section 7.3). A minimum of one week is provided to decide whether the volunteer would like to participate. Volunteers will not be contacted if they do not respond to the sent information brochure. Upon arrival for the first visit, the participants will have to sign an informed consent before screening can start. If participants withdraw from the study after the screening, these results will be destroyed. Participants can make at any time an appeal to the independent doctor that has been appointed to this study. Participants will be informed that their decision to participate is voluntary and they can withdraw at any time without giving a reason. At the end of the study, participants will have the opportunity to be informed about their individual results and the group results.

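### Section 9.2 leaves out an intervention when a VAS score is missing, which costs that subject's within-subject treatment contrast: an avoidable precision loss, of unknown size, on the secondary VAS endpoints only

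*Combined protocol and SAP*

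**What the plan says.** Section 9.2 plans a repeated measures ANOVA of the VAS scores with treatment, time and their interaction. If the yoghurt effect is significant by Wilks' Lambda, "the treatments will be compared based on pairwise comparison with a Tukey post hoc test". The missing-data rule is one sentence: "Missing values of the secondary study parameter will cause the intervention to be left out, due to the use of ANOVA".

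The structure it applies to is set out elsewhere:
- Section 7.2: "All 35 participants receive two treatments of one day each, following a cross-over design".
- Section 7.3: nine attributes are scored at 12 time points on each test day.
- Section 7.1.2: "The VAS scores will be compared in time between intervention and control within a subject".
- Section 9: subject ID, test day, treatment and time are all planned as variables in the data set.

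No imputation, mixed model or sensitivity analysis is planned for the VAS scores, and no VAS missing rate or VAS power is given. The only allowance for loss is in section 4.4, for food intake: "According to this power calculation, 31 subjects will need to complete the study", with 35 recruited.

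**The concern.** With one food-intake value per day, a missing value necessarily breaks the pair, so the rule in section 9.1 follows from the data. With 12 VAS scores per day it does not: one skipped score leaves 11 others for that attribute on that day and 12 on the other day. The rule discards the day, the remaining day has no partner, and the subject contributes nothing to the treatment comparison. The only reason offered is the choice of ANOVA, which is a choice of method and not a limit of the data.

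Satiety and GI symptoms are both secondary objectives. Fewer contrasts mean wider intervals for them, and imprecision makes it easier to report no difference in GI symptoms.

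**Working it through.** **1. The plan's own figure.** Section 4.4 uses a paired difference of 82 kcal with SD 156 kcal, two-sided alpha 0.05 and 80% power.
- Normal start: (156/82)² × (1.96 + 0.84)² = 3.619 × 7.84 = 28.4, so 29.
- Iterating with t values at 30 df: 3.619 × (2.042 + 0.854)² = 30.4, so 31.

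This reproduces the plan's 31 and is not in dispute. It concerns food intake only.

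**2. What one missing score costs.** Each subject has 12 × 2 = 24 scores per attribute. If one is missing, the written rule removes that day's 12 cells, 11 of them recorded. The other day's 12 scores then have no within-subject partner. So 11 + 12 = 23 recorded scores do no work in the treatment contrast. If the rule means that the whole subject is dropped, the contrast is lost just the same.

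**3. How many contrasts are lost.** Let m be the chance that a score is missing. The documents do not give m, so every value below is an assumption. Deletion is taken as per attribute.
- Independent missingness: share kept = (1 − m)^24.
- Missing scores clustered within subject (beta-binomial, ICC 0.10, so the two parameters sum to 0.9/0.1 = 9): share kept = product over i = 0 to 23 of (9(1 − m) + i)/(9 + i).
- Contrasts lost = 35 × (1 − share kept). SE ratio = 1/√(share kept).

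| m | Kept, independent | Lost of 35 | SE ratio | Kept, ICC 0.10 | Lost of 35 | SE ratio |
|---|---|---|---|---|---|---|
| 0.1% | 0.976 | 0.8 | 1.012 | 0.988 | 0.4 | 1.006 |
| 0.5% | 0.887 | 4.0 | 1.062 | 0.941 | 2.1 | 1.031 |
| 1% | 0.786 | 7.5 | 1.128 | 0.886 | 4.0 | 1.062 |
| 2% | 0.616 | 13.4 | 1.274 | 0.785 | 7.5 | 1.129 |

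**4. Whether the loss is avoidable.** Take the mean treatment difference over the eight post-yoghurt times (t = 105 to 210). Assume variances of 200 (subject), 100 (subject by day) and 150 (residual) mm², and a 15-minute correlation of 0.7. Generalised least squares on all recorded scores, with independent missingness, then gives SE ratios of 1.0001, 1.0002 and 1.0004 at 0.5%, 1% and 2%. Nearly all of the loss in step 3 comes from the rule rather than from the missing scores.

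**5. Where a mixed model helps and where it does not.** If the 35 − 31 = 4 dropouts that section 4.4 allows for all lost their contrast, the SE ratio would be √(35/31) = 1.063. Had all four left after the t = 150 form on their second day, using all recorded scores would bring it to 1.004 (same assumed variances). Had they never attended a second day, no model could recover their contrasts. The first case favours the fix, and nothing in the documents makes it the likelier one.

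**The case against.** The strongest reply is that the loss may be negligible. Scores are taken on site during a test day of about four hours, and "The scoring forms will be collected immediately so that they cannot be used as a reference for later scorings". At 0.1% missing, fewer than one contrast in 35 is lost and the standard error rises by about 1%. The rule is stated in advance, matches the complete-pair rule for the primary endpoint, and applies to secondary endpoints of a study described as explorative. All of that stands. It limits the priority of the point, but does not supply a reason to discard recorded scores.

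The sentence is also unclear: the term intervention is not defined there, and deletion per attribute is an inference. The contrast is lost whether a day or a subject is removed, but the counts above depend on the per-attribute reading. A reader might infer deletion across all nine attributes, which would cost far more. The text does not say that, so no weight is put on it.

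A reader might also infer that the rule biases the GI comparison by removing people who stop because of symptoms. That is possible, but the documents say nothing about why scores would be missing, so it is not shown. Nor does the rule hide harms. It governs the ANOVA only. The pain-based halting rule in sections 6.4 and 10.4 does not depend on that analysis, and section 8.2.1 provides separately that "All AEs reported spontaneously by the subject or observed by the investigator or his staff will be recorded".

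**Conclusion.** The point holds as an avoidable loss of precision on the secondary VAS endpoints, for the sponsor to consider. It is an inefficiency and does not invalidate the analysis. Its size is unknown: from about 1% on the standard error at 0.1% missing per score to 13–27% at 2%. The range rests on assumed missing rates, per-attribute deletion, and missingness between independent and moderately clustered (ICC 0.10). The near-zero end is plausible given supervised scoring. The food-intake analysis is untouched, because it has one value per day and its own rule. The documents support neither a claim of bias nor a claim that four contrasts will be lost in a recoverable way: the dropout allowance covers losses of any kind.

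**What to change.** In section 9.2, replace the repeated measures ANOVA, its Wilks and Tukey follow-up (with two treatments there is only one pair to compare) and the missing-value sentence with text along these lines:

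> Each VAS attribute is analysed with a linear mixed model fitted by REML. Fixed effects are treatment, time, treatment-by-time and test day, with a random subject effect. The within-day covariance is [one named structure in which correlation falls with time separation], with Satterthwaite or Kenward-Roger degrees of freedom. All recorded scores are used; no test day or subject is removed because a score is missing. The mean treatment difference over the post-yoghurt time points is reported with a 95% confidence interval, together with the treatment-by-time test.

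The post-yoghurt mean is an example. The team may choose another contrast, but should name it in advance. The present check of distributional assumptions should stay.

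The cost is low, though more than a change of wording: the VAS model is replaced and a test-day term added. No new visits, subjects or measurements are needed, since the variables are already planned. The team must confirm that the software named in section 9 fits the chosen covariance and degrees-of-freedom method, or name other software. The downsides are that the model assumes missing at random, which fails if stopping depends on unrecorded symptoms; that the covariance must be fixed beforehand; and that a subject with only one test day still yields no within-subject contrast.
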